## 5.6. Accountability of Study Drug

The investigator and investigational site staff are responsible for maintaining an accurate inventory and accounting of study drug. A record of all vials and tablets of study drug received and administered will be maintained on an investigational drug inventory form provided by the Sponsor or an equivalent drug inventory form. The following information will be recorded:

- Date and quantity of study drug received
- Date and quantity of study drug dispensed from the pharmacy per patient
- Date and quantity of study drug administered to each patient
- Date and quantity of study drug destroyed (if prepared and dispensed, but not administered for any reason, the study drug may not be returned to inventory)

• Date and quantity of study drug returned to sponsor, if applicable

Each shipment of study drug will contain an invoice describing the amount of drug shipped to the investigational site. The information on the invoice will be verified against the actual amount of drug received, after which the investigator or the investigator's designee will place the invoice in the investigator's file.

The sponsor's monitor will reconcile the information on the investigational drug inventory form with the actual amount of study drug remaining at each site on a routine basis. At the conclusion of the study, the monitor will either package and ship all unused vials of study drug back to Sponsor for destruction or document the destruction, in accordance with local regulations and institutional policy. Following use, empty vials of study drug may be destroyed according to local regulatory and environmental requirements. A record of any such destruction will be placed in the investigator's file.

# 6. Schedule of Assessment

# **6.1.** Schedule of Assessments: Heregulin Positive Patients

Procedure Screening Visit		Cycle 1 				Cycle 2 				Additional Cycles 				Every 8 weeks	30 Day	Every 2 months
	Wk 1	Wk 2	Wk 3	Wk 4	Wk 1	Wk 2	Wk 3	Wk 4	Wk 1	Wk 2	Wk 3	Wk 4	from first dose 	Follow -Up 	from FU Visit	
Informed Consent	X															
HRG Testing	$X^1$															
Tumor Biopsy 	X															
Medical history	$X^1$															
Demographics	X 															
Vital signs	$X^2$	X		X		X		X		X		X			X	
ECOG PS	$X^2$	X				X				X					X	
CBC	$X^2$	X		X		X		X		X		X			X	
Serum chemistry	$X^2$	X		X		X		X		X		X			X	
Coagulation profile	$X^2$	X				X				X					X	
Pregnancy test	$X^2$														X	
ECG	X 	$X^{16}$				$X^{16}$				$X^{16}$						
ECHO/MUGA 	$X^1$													X	$X^{20}$	
Archived tumor, if available	X															
Fresh tumor biopsy	$X^{11}$															
Serum for seribantumab PK 		$X^{7a}$		$X^{7b}$		$X^{7b}$		$X^{7b}$								
Serum for Ig 		X				X				X					X	
Serum for biomarkers 		X				X				X						
Plasma for ESR1 testing		$X^{21}$													X	
Plasma for fulvestrant PK		$X^{12}$		$X^{12}$		$X^{12}$		$X^{12}$								
Concomitant meds	$X^1$	X		X		X		X		X		X			X	
Seribantumab dosing		X		X		X		X		X		X				
Fulvestrant dosing		X		X		X				X						
SAE/AE assessment and reporting 							•	Continuo	us monito	oring						
Hospitalization reporting 		X		X		X		X		X		X			X	X
Disease evaluation 	$X^1$													X 	X	
Overall Survival Reporting																$X^{15}$

Proprietary and Confidential Page 43 of 65

-  Procedures to be completed within 28 days of signing the **main** informed consent form
-  Procedures to be completed within 7 days of first dose of Seribantumab
-  Two independent readings at least 5 minutes apart
-  Evaluations may be performed  $\pm$  1 week from the scheduled date of visit
-  Any patient that comes off treatment for reasons other than progressive disease, will have a scan to assess disease status at the time of treatment discontinuation and additional scans every 8 weeks (+/- 1 week) until investigator-assessed PD
-  All procedures should occur ±2 calendar days from scheduled date of visit
-  Seribantumab PK: all patients; in relation to seribantumab infusion
  - a C1W1: immediately after the end of the Seribantumab infusion (+15 mins)
  - b C1W3, C2W1, C2W3: pre-dose
-  Immunogenicity samples should be collected for all patients prior to dosing.
-  In the event a patient experiences an infusion reaction at any point in the study, an anti-Seribantumab antibody assay will be taken within 24 hours of the event, in addition to the scheduled time-points. For patients who experience a Grade 3 or 4 infusion reaction to Seribantumab, an anti-Seribantumab antibody titer will be taken as close to the onset of the infusion reaction as possible, at the resolution of the event and 28 days (+/- 2 days) following the event.
-  Disease evaluation per RECIST version 1.1.
-  Tumor sample is to be collected for all HRG positive patients that receive HRG results for eligibility based on testing of archived samples. An additional sample is not required for patients who underwent a fresh biopsy for eligibility testing.
-  Fulvestrant PK: all patients: prior to seribantumab injection
-  Serum for biomarkers should be collected pre-infusion on week 1 of each cycle for all patients
-  End of treatment (30-day Follow-up) visit should be completed within 30 days of the last dose of study drug
-  Should patients refuse or drop out of survival follow-up, attempts should be made to obtain any death information available via public records.
-  One reading prior to infusion with seribantumab.
-  AE/SAE collection to be included. S/AE assessment and reporting will proceed as outlined in Sections 9.2 and 9.3
-  All patient hospitalizations and/or hospital visits should be collected, whether or not associated with an adverse event.
-  In addition to the timepoints noted, MUGA or Echocardiogram should be performed post-screening for any study patient who develops symptoms consistent with new onset of congestive heart failure.
-  Unless performed within the last 4 weeks as part of assessments in the previous cycle
-  Sample to be collected prior to any study treatment.

Proprietary and Confidential Page 44 of 65

## 6.2. Schedule of Assessments: HRG Negative Patients

Procedure	Screening Visit
Informed consent 	X
SAE assessment and reporting 	X
Cancer Diagnosis History 	X
Prior Anti-Cancer Therapies 	X
Prior Radiotherapies 	X

<sup>1 To be completed prior to any study-related procedures.

# 6.3. Screening and Baseline Visit

All procedures for screening and baseline are outlined in Section 6.1. The window for screening procedures begins after signing the main consent form. For further descriptions of the clinical and laboratory assessments required, please refer to Section 7 and 8 respectively.

## 6.3.1. RNA-ISH Heregulin Testing

All patients must submit a tissue sample for RNA-ISH testing of heregulin levels as soon as possible following signing the informed consent form, as this will determine patient eligibility for treatment randomization and subsequent screening procedures. The HRG RNA-ISH assay can be used to measure mRNA expression on tissue slides obtained from formalin-fixed paraffin embedded archived blocks, core biopsies or fine needle aspirates; therefore, any of these methods of collection is acceptable for testing.

If archive tissue is being used for eligibility testing, the most recent sample available should be submitted. Heregulin testing can be performed on tissue obtained at the following times:

- At the time of initial diagnosis
- At the time of metastatic diagnosis
- or on tissue obtained from a fresh tumor biopsy.

If collection of fresh tissue is required in order to provide adequate tissue for testing, attempts should be made to acquire tissue from a tumor in a non-significant risk location, as determined by the investigator. As a general guideline, if the selected procedural location of the core needle biopsy or FNA has an established serious complication rate of >2% at the institution completing the procedure, this is considered a high risk procedure and should be avoided. Primary tumor samples and samples obtained from metastatic sites are both acceptable.

Preparation of samples for HRG testing should be conducted in accordance with the laboratory manual. Specific procedures for the collection and processing of bone biopsies are provided in the manual.

Samples will be processed and analyzed at a central facility where they are scored by a pathologist as specified in the lab manual with a turnaround time of no longer than 7 days from date of receipt by the central lab. Any patient who scores positive (a score of  $\geq 1+$ ) for HRG mRNA will be eligible for the study and should continue with screening procedures.

<sup>2 Any serious adverse events considered by the Investigator to be directly related to screening procedures (i.e. related to screening biopsy) should be collected and reported from the time of informed consent up to receipt of HRG results.

<sup>3 Minimal medical history will be collected from all HRG negative patients.

#### **6.3.2.** Heregulin Negative Patients

Any patient whose tissue is negative (score of 0) for heregulin as determined by the RNA-ISH test will be considered a screen failure. Minimal medical history for HRG negative patients will be collected as outlined in Section 6.2.

### 6.4. On-Study Visits

Patients who are confirmed to meet all inclusion and exclusion criteria will be randomized via an IWRS. Randomization must occur within 7 days of first dose (cycle 1 day 1).

All on-study procedures and assessments are outlined in Section 6.1. During the treatment period, a window of  $\pm 2$  days will apply to all visits, unless otherwise stated.

#### 6.5. End of Treatment Visit

When it is decided that a patient will stop receiving treatment on this study, an End of Treatment visit must be completed within 30 days of last dose of study drug. All End of Treatment procedures and assessments are outlined in Section 6.1.

## 6.6. Survival Follow-up

Survival data will be collected via telephone or clinic visits every 2 months (±10 days) from the date of the 30-day follow-up visit until death, loss to follow-up, withdrawal of consent, or study termination by the Sponsor. In addition, any new anti-cancer therapies and procedures should be collected and documented. All survival information will be captured using the electronic data capture (EDC) system. Should patients refuse or drop out of survival follow-up, attempts should be made to obtain any death information via public records whenever possible.

## 7. Clinical Procedures and Assessments

All following clinical procedures should be performed in accordance with the schedule of assessments outline in Section 6.1.

### 7.1. Medical History and Demographics

Demographic information including age, date of birth, race, ethnicity and gender will be collected

A medical history will be collected including all pertinent prior medical conditions, surgeries or other medical procedures, allergies, and concomitant medications.

### 7.2. Adverse Event and Hospitalization Assessment Reporting

Investigators should complete all routine and standard of care assessments to evaluate for toxicity and symptoms of drug-induced adverse events. This may include, but is not limited to, verbal reports from the patient and/or caregiver, physical examination and laboratory findings. Adverse events should be reported throughout the course of the study beginning at the time of signing the main study informed consent form, until the study termination visit, and followed through to resolution as detailed in Section 9.

Adverse events and serious adverse events should not be reported for patients that only sign the biomarker informed consent form unless the event is considered by the investigator to be directly related to a study procedure (i.e. tumor biopsy for heregulin testing).

In addition, information on patient hospitalizations and/or unscheduled hospital visits should also be collected in the eCRF, whether or not associated with an adverse event.

# 7.3. Vital Signs

Vital signs should include height (screening only), weight, resting blood pressure, pulse, respiratory rate, and temperature.

#### 7.4. Performance Status Assessment

The Eastern Cooperative Oncology Group (ECOG) performance status (PS) will be obtained by the PI or his/her designee by questioning the patient about their functional capabilities.

# 7.5. Electrocardiogram (ECG)

A 12-lead electrocardiogram (ECG) will include a description of the cardiac rate, rhythm, interval durations, and an overall impression. QTc should be calculated using the Fridericia method (QTcF). ECGs will be performed for all patients at screening to rule out clinically significant abnormalities. For randomized patients, ECGs will be performed on week 1 of each cycle prior to dosing with seribantumab.

# 7.6. Echocardiogram or Multiple Gated Acquisition Scan

An echocardiogram (ECHO) or multiple gated acquisition scan (MUGA) will be performed to determine ejection fraction. The same procedure (ECHO or MUGA) performed during screening to determine the ejection fraction should be employed at subsequent visits. In addition to the required timepoints, ECHO or MUGA should be performed post-screening at any time for any study patient who develops symptoms consistent with new onset of congestive heart failure.

#### 7.7. Disease Evaluation

Tumor response will be evaluated by the local radiologist according to the Response Evaluation Criteria in Solid Tumors (RECIST) version 1.1 (Eisenhauer et al., 2009) to establish disease progression by CT or MRI. In addition, other radiographic or scintigraphic procedures (such as radionuclide bone scans), as deemed appropriate by the investigator, will be performed to assess sites of neoplastic involvement. The same method of assessment must be used throughout the study. Please refer to image acquisition guidelines for the requirements for image collection and scanner qualification. Investigators should choose target and non-target lesions in accordance with RECIST v1.1 guidelines. Follow-up measurements and overall response should also be in accordance with these guidelines. To be assigned a status of confirmed partial response (PR) or complete response (CR), changes in tumor measurements must be confirmed by repeated assessments that should be performed ≥30 days after the criteria for response are first met.

Disease should be assessed every 8 weeks (±5 days) from randomization regardless of treatment schedule until investigator-assessed progression. In cases where there is a suspicion of disease progression prior to the next scheduled scan, an unscheduled assessment should take place. All patients who come off study treatment prior to disease progression for reasons including patient or physician decision or unacceptable toxicity will continue to undergo tumor assessments every 8 weeks (±5 days) until investigator-assessed progression of disease.

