on the date of randomization. Patients starting a new anti-cancer treatment prior to documented PD will be censored at the date of the last observed tumor assessment prior to start of the new treatment. Patients with documented PD or death after an unacceptable long interval (i.e., 2 or more missed or indeterminate scheduled assessments) will be censored at the time of the last observed tumor assessment date. PFS will be calculated as the date of the event/censor minus date of randomization plus one.

The primary analysis will be performed using a stratified log-rank test comparing the PFS difference between two treatment arms. The final PFS analysis will preserve the 1-sided alpha at 0.10. Stratification factors will include bone-only disease (yes, no) and geographic status (US, and non-US). Kaplan-Meier estimates will be used to display PFS time graphically. Cox proportional hazards model will be used to estimate hazard ratio and the corresponding 80% confidence interval. Median PFS event times and 80% confidence interval will be computed as well.

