#### 4.4. Patient Discontinuation

A patient may withdraw from the study at any time and for any reason. It is intended that patients will be treated until investigator-determined progressive disease (radiologic or clinical deterioration) or unacceptable toxicity. Some possible reasons for withdrawal from treatment include, but are not limited to the following:

- Progressive neoplastic disease per RECIST v1.1
- Clinical deterioration
- Adverse event, including treatment being withheld for 21 consecutive days without resolution of toxicities to grade 1 or baseline value

- Protocol violation / non-compliance
- Withdrawal of consent
- Investigator or sponsor decision
- Patient is lost to follow-up

When a patient is discontinued from treatment for any reason, they are to undergo the assessments in the End of Treatment visit within 30 days of the last dose. All patients who discontinue treatment as a result of an adverse event must be followed until resolution or stabilization of the adverse event. At the time a patient withdraws from study treatment, an attempt should be made to determine the reason(s) for discontinuation. The patient will continue to be followed for survival information every 2 months after completion of the End of Treatment visit. All patients, including patients who discontinue treatment for reasons other than progressive disease per RECIST 1.1, should undergo a scan to assess disease status at the time of treatment discontinuation, and again 8 weeks following treatment termination.

If a patient does not return to the clinic for the end of treatment visit or is not reached for overall survival follow-up, at least 3 documented attempts, including one via certified mail, should be made to contact the patient. If there is no response to these requests, the date of death should be captured from public records.

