## **3. ENDPOINTS**

## 3.1 Progression-Free Survival – Investigator Assessed

Investigator Assessed (IA) tumors assessments are those determined by the investigator. PFS is defined as the number of months from the date of randomization to the date of death or documented (objective) disease progression via RECISTv1.1, whichever occurs earliest. Length of PFS will be calculated in days and reported in months.

[Progression/Death/Censor Date - Randomization Date + 1] / 30.4375.

The tumor assessment (i.e., scan dates) will be used for progression/censor date not the date corresponding to the determination of overall response. When multiple dates occur for assessing target, non-target, and new lesions the following rule will be applied:

- If documented disease progressions, the *first* available date will define the tumor assessment date
- If censored, the *last* available date will define the tumor assessment date.

Per protocol tumor assessments are scheduled to be performed every 8 weeks ( $\pm$  7 days) from day of first dose until investigator-assessed progression, in addition to a 30-day follow-up.

**Censorship**: In general, patients are censored at the date of the last tumor assessment that verified lack of disease progression if they are last known to be alive, on-treatment or within 30 days following treatment discontinuation, and progression-free. Censoring is explicitly described below and in table 1. Patients that do not experience progression or death by the time of analysis (data cut-off) will be censored at the date of last tumor assessment defined by any overall response other than "not evaluable".

- Patients with an inadequate/incomplete baseline tumor assessment will be censored at the date of randomization
- Patients with no tumor assessment after dosing will be censored at the date of randomization unless death occurred prior to the first planned assessment (in which case the death is an event)
- Patients with at least one on-study disease assessment who discontinue treatment without documented disease progression or death are censored at the date of the last tumor assessment

There are two exceptions.

- $\circ$  Documented progression or death  $\leq$  30 days after treatment discontinuation then progression or death is an event

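### Conflicting scan calendars leave open whether a progression or death long after stopping treatment counts as an event in the primary PFS analysis

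*Protocol*

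**What the plan says.** **Anchor and window.** Protocol 7.7 reads "Disease should be assessed every 8 weeks (±5 days) from randomization regardless of treatment schedule until investigator-assessed progression". The synopsis and 3.1 give the same anchor and the same ±5 days. The schedule table in 6.1 heads its 8-weekly column "from first dose", and footnote 4 allows ± "1 week from the scheduled date of visit". SAP 3.1 follows the table: every 8 weeks, ±7 days, "from day of first dose until investigator-assessed progression, in addition to a 30-day follow-up". Protocol 3.1 lets treatment start up to 7 days after randomization, so the two anchors need not coincide.

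**After stopping before progression.**
- The synopsis, 3.1 and 7.7 continue 8-weekly assessments until investigator-assessed progression.
- Footnote 5 of 6.1 adds a scan at discontinuation, then "additional scans every 8 weeks (+/- 1 week) until investigator-assessed PD". The table also marks a disease evaluation at the 30-day visit.
- Section 4.4 says patients "should undergo a scan to assess disease status at the time of treatment discontinuation, and again 8 weeks following treatment termination". It states no scan after that.
- SAP 3.1 and Table 3.1 censor a patient who discontinues without progression at an earlier scan, unless progression or death follows within 30 days. A note to Table 3.1 refers to follow-up scans up to 4 weeks after the last dose.

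**Missed scans.** The protocol synopsis censors progression or death that follows "2 or more missed or indeterminate scheduled assessments". SAP 3.1 has the same rule and adds that they be consecutive. Neither document defines a missed assessment in days or says which calendar sets what was scheduled.

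**The concern.** SAP 3.1 dates PFS events by the scan, and both documents censor an event that follows two or more missed scheduled scans. The calendar is therefore part of the endpoint definition. If the documents disagree about which scans were due, they also disagree about which were missed, and about whether a later progression or death counts.

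The anchor and window conflict moves scan dates by days. The post-treatment conflict can change a patient from event to censored. The primary test rests on only 58 events, and scans that a site did not do because it followed 4.4 cannot be recovered at analysis.

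**Working it through.** **Design basis (protocol 10.2).** HR 0.57, one-sided alpha 0.10, 80% power, 1:1. Schoenfeld: d = 4(1.2816 + 0.8416)² / (ln 0.57)² = 18.03 / 0.316 = 57.1, so 58 events, as stated. Power at 58 events is 80.5%.

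**Anchor and window, days from randomization.** The text window for scan k is 56k ± 5. The table and SAP window is L + 56k ± 7, where L is the lag to first dose, 0 to 7 days.

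| Scan | Text | Table/SAP, L = 0 | Table/SAP, L = 7 |
|---|---|---|---|
| 1 | 51–61 | 49–63 | 56–70 |
| 2 | 107–117 | 105–119 | 112–126 |
| 3 | 163–173 | 161–175 | 168–182 |

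The largest excess is 70 − 61 = 9 days, and it does not grow from scan to scan. If lags are uniform on 0–7 days and scans uniform within ±7 days (assumptions), 47 of 120 lag-and-day combinations (39%) fall outside the text window.

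**Effect on the test.** A simulation used 2,000 trials of 40 per arm, exponential PFS with medians 4 and 7 months, 16-month uniform accrual, a cut at the 58th event and an unstratified log-rank test. Power was 79.3% (randomization ±5) and 79.5% (first dose ±7). The observed control median was 4.97 and 4.98 months. The difference is within simulation error.

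**Post-treatment rule: one illustrative patient.** She has a scan on day 56, stops for toxicity on day 60 with a scan that day, is scanned again on day 116, starts no new anticancer treatment, and dies on day 300 with no further scan. No scan shows progression.

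| Governing passage | Scans due after day 116 | PFS outcome |
|---|---|---|
| Protocol 4.4 | none | none missed: event, day 300 |
| Protocol 7.7 | 168, 224, 280 | three missed: censored, day 116 |
| Protocol 6.1 footnote 5, counted from the stop | 172, 228, 284 | three missed: censored, day 116 |
| SAP Table 3.1 | not relevant | 300 − 60 = 240 days after stopping, beyond 30: censored, day 60 at the latest |

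The day-116 scan also lies inside the 7.7 window for scan 2 (107–117), so the early visits do not cause the disagreement.

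**A fully compliant patient.** Suppose instead that she is scanned on the 7.7 calendar and progression is found on day 224. Under the synopsis definition this is an event. Under SAP 3.1 it comes 224 − 60 = 164 days after stopping and is censored. Scans until progression would then be collected but not used in the primary analysis.

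**Number affected.** The documents give no rate of stopping before progression, so this cannot be computed. As a range only: if 5% to 25% of the 58 events were lost and not replaced (assumption), power would be 79.0% to 71.6%. Because the analysis waits for 58 events, the first effect would be a later data cut.

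**The case against.** **The anchor and window differences are trivial.** This stands. They are a matter of days, do not accumulate, should be similar in both arms under blinding, and leave power unchanged. Nor does any passage treat a scan outside its window as missed, so a 7–9 day shift cannot by itself trigger the two-missed-scans rule.

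**Section 4.4 is incomplete wording, not a rival rule.** This is partly right. It never says that scanning ends, its two scans match the first two in footnote 5, and four other places require scans until progression. A reader might infer that most later progression among early stoppers would go unscanned; that needs a site to follow 4.4 alone against those four statements. What remains is that 4.4 is the section on discontinuation and, read as written, makes nothing due after the second scan.

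**The SAP conflict belongs to a larger problem.** This is also right in part. The SAP names protocol 02-03-10, not 02-02-10, and describes a phase 3, 2:1 trial of exemestane or fulvestrant with 195 events. But 7.7, 6.1 and 4.4 all sit inside the protocol that sites follow, and 10.5.1 leaves censoring detail to the SAP. Replacing the SAP alone would not settle it.

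**Few patients may be affected.** The synopsis already censors at the start of new anticancer treatment before progression, so the conflict bites only for patients who stop early and start none. The documents do not say how many that is.

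**Two stronger readings are not supported.** A reader might infer that stopping treatment brings the progression date forward substantially. That requires two 8-weekly calendars run in parallel plus extra scans, which no passage asks for. With exponential PFS (median 4 or 7 months) and stopping uniform over days 14–168 (assumptions), mean delay to detection is about 28 days on the fixed calendar. It is 25.4 or 26.4 days if the patient moves to a calendar counted from the stop with a 30-day scan, and 29.5 or 28.8 days without a separate 30-day scan. A reader might also infer a bias between arms from the diarrhea rates with exemestane in protocol 1.5.3.1 (50.0% against 23.7%). Those are events of any relationship, not discontinuations. The same section reports fewer serious events on seribantumab (12.5% against 18.6%), and no discontinuation rate by arm is given.

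**Conclusion.** The concern holds, with its weight on the post-treatment rule. The protocol contains two scan calendars, up to 9 days apart at the window edge, with negligible effect on power. It also contains different statements about scanning after early discontinuation, and the SAP adds a 30-day limit that the protocol's PFS definition does not have. Under these passages the same patient can be an event or be censored, at dates months apart. This rests on the text alone; the illustrative patient only makes it concrete. No count of affected events, direction of bias or corrected sample size follows from the documents. It should be resolved because the endpoint is primary, the event number is small and the remedy is mostly wording.

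**What to change.** Reconcile protocol 4.4, 6.1 (column header and footnotes 4 and 5) and 7.7, and SAP 3.1:

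1. One calendar, every 8 weeks from randomization as 7.7 already states, which is also time zero for PFS.
2. One window, either ±5 or ±7 days, used everywhere.
3. The calendar continues unchanged after treatment stops, until investigator-assessed progression. The discontinuation and 30-day evaluations need not be altered, but should be described as not resetting it.
4. Missed scheduled assessments are counted on that calendar, with the rule expressed in days.
5. SAP 3.1 and Table 3.1 treat progression or death after discontinuation as the protocol's PFS definition does, without the 30-day limit. Without this step, the scans required by step 3 would not reach the primary analysis.

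The cost is amendment wording in three protocol sections and a revision of the SAP's censoring text and table. The SAP needs rewriting for this design in any case. The protocol already requires scans until progression in four places, so no new scanning burden is intended.
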